4.1.2 Secondary Effectiveness

- Mean Binocular photopic DCNVA (logMAR) at 40 cm
 - Proportion of subjects who respond “Never” to Q1 of the spectacle use questionnaire (IOLSAT)
- [REDACTED]

4.2 Effectiveness Hypotheses

4.2.1 Primary Effectiveness Hypotheses

The null and alternative hypotheses for the first primary effectiveness endpoint are:

$$H_0: \mu_{Vivity} - \mu_{Monofocal} \geq \Delta$$

$$H_1: \mu_{Vivity} - \mu_{Monofocal} < \Delta$$

where μ_{Vivity} and $\mu_{Monofocal}$ are the means for binocular BCDVA for test (Clareon Vivity/Vivity Toric IOL) and comparator (Clareon Monofocal/Clareon Toric IOL), respectively, at Visit 1 (90 to 180 days postoperatively), and Δ is the noninferiority margin set at 0.1 logMAR.

The null and alternative hypotheses for the second primary effectiveness endpoint are:

$$H_0: \mu_{Vivity} \geq \mu_{Monofocal}$$

$$H_1: \mu_{Vivity} < \mu_{Monofocal}$$

where μ_{Vivity} and $\mu_{Monofocal}$ are the means for binocular DCIVA for test (Clareon Vivity/Vivity Toric IOL) and comparator (Clareon Monofocal/Clareon Toric IOL), respectively, at Visit 1 (90 to 180 days postoperatively).

4.2.2 Secondary Effectiveness Hypotheses

The null and alternative hypotheses for the first secondary endpoint are:

$$H_0: \mu_{Vivity} \geq \mu_{Monofocal}$$

$$H_1: \mu_{Vivity} < \mu_{Monofocal}$$

[figure not shown]
where μ_{Vivity} and $\mu_{Monofocal}$ are the means for binocular DCNVA for test (Clareon Vivity/Vivity Toric IOL) and comparator (Clareon Monofocal/Clareon Toric IOL), respectively, at Visit 1 (90 to 180 days postoperatively).

The null and alternative hypotheses for the second secondary endpoint are:

$$H_0: p_{Vivity} \leq p_{Monofocal}$$

$$H_1: p_{Vivity} > p_{Monofocal}$$

where p_{Vivity} and $p_{Monofocal}$ are the proportion of subjects who respond “Never” to Q1 of the IOLSAT, for test (Clareon Vivity/Vivity Toric IOL) and comparator (Clareon Monofocal/Clareon Toric IOL), respectively, at Visit 1 (90 to 180 days postoperatively).

4.3 Statistical Methods for Effectiveness Analyses

4.3.1 Primary Effectiveness Analyses

The FAS will be used for the primary statistical analyses for both primary effectiveness endpoints. [REDACTED]

4.3.1.1 Mean Binocular photopic BCDVA (logMAR) at 4 m

Analysis of the first primary effectiveness endpoint (BCDVA) will be based on a two-sample t-test assuming equal variances, [REDACTED]. The difference in means (Vivity IOL minus Monofocal IOL) and the associated two-sided 90% confidence interval will be presented. Noninferiority is demonstrated if the one-sided p-value for the t-test is less than 0.05 or, equivalently, the upper limit of the two-sided 90% confidence interval is less than the noninferiority margin. A two-sided 95% confidence interval will also be provided for descriptive purposes.

[REDACTED]

In addition, the following descriptive statistics (number and percentage in the category) will be provided for each IOL group:

- logMAR categories: the number and percentage of eyes (for monocular endpoints)/subjects (for binocular endpoints) with visual acuity of
 - 0.0 logMAR or better: ≤ 0.00 logMAR
 - 0.1 logMAR or better: ≤ 0.10 logMAR
 - 0.2 logMAR or better: ≤ 0.20 logMAR
 - 0.3 logMAR or better: ≤ 0.30 logMAR
- Snellen categories: the number and percentage of eyes (for monocular endpoints)/subjects (for binocular endpoints) with visual acuity of
 - 20/20 Snellen or better: ≤ 0.04 logMAR
 - 20/25 Snellen or better: ≤ 0.14 logMAR
 - 20/32 Snellen or better: ≤ 0.24 logMAR
 - 20/40 Snellen or better: ≤ 0.34 logMAR

4.3.1.2 Mean Binocular photopic DCIVA (logMAR) at 66 cm

Analysis of the second primary effectiveness endpoint (DCIVA) will be based on a two-sample t-test assuming equal variances, with a type I error rate of 5%, 1-sided. The difference in means (Vivity IOL minus Monofocal IOL) and the associated two-sided 90% confidence interval will be presented. Superiority is demonstrated if the one-sided p-value for the t-test is less than 0.05 or, equivalently, the upper limit of the two-sided 90% confidence interval is less than 0. A two-sided 95% confidence interval will also be provided for descriptive purposes.

In addition, the descriptive statistics (number and percentage in the category) will be provided for each IOL group described in Section 4.3.1.1.

4.3.2 Secondary Effectiveness Analyses

The FAS will be used for the primary statistical analyses for both secondary effectiveness endpoints. [REDACTED]

[figure not shown]
4.3.2.1 Mean Binocular photopic DCNVA (logMAR) at 40 cm

[figure not shown]
Analysis of the first secondary effectiveness endpoint (DCNVA) will be based on a two-sample t-test assuming equal variances, with a type I error rate of 5%, 1-sided. The difference in means (Vivity IOL minus Monofocal IOL) and the associated two-sided 90% confidence interval will be presented. Superiority is demonstrated if the one-sided p-value for the t-test is less than 0.05 or, equivalently, the upper limit of the two-sided 90% confidence interval is less than 0. A two-sided 95% confidence interval will also be provided for descriptive purposes.

[figure not shown]
In addition, the descriptive statistics (number and percentage in the category) will be provided for each IOL group described in Section 4.3.1.1.

[figure not shown]
4.3.2.2 Proportion of subjects who respond “Never” to Q1 of the spectacle use questionnaire (IOLSAT)

[figure not shown]
A two-sided 90% confidence interval for the difference in proportions (Vivity IOL – Monofocal IOL) will be calculated using the Miettinen-Nurminen method (1985), and Vivity IOL will be determined to be superior to Monofocal IOL if the lower boundary of the confidence interval is greater than zero. This is equivalent to using a type I error rate of 5%, 1-sided. A two-sided 95% confidence interval will also be provided for descriptive purposes.

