7.4 Rationale for Choice of Comparator Product

The test group includes subjects previously implanted bilaterally with Clareon Vivity/Clareon Vivity Toric IOLs. The control (comparator) group includes subjects previously implanted bilaterally with Clareon Monofocal/Clareon Toric IOLs. Both groups were chosen to generate clinical data to augment parent model data and support the clinical benefits with model-specific data. Clareon Monofocal was chosen as the control (comparator) to support clinical benefit statements in which the performance of Clareon Vivity/Vivity Toric is compared to a monofocal IOL.

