8.2 Exclusion Criteria

Subjects fulfilling **any** of the following criteria are not eligible for participation in this study.

- 1. Women of childbearing potential, defined as all women who are physiologically capable of becoming pregnant and who are not postmenopausal for at least 1 year or are less than 6 weeks since sterilization, are excluded from participation if any of the following apply:
 - a. they are currently pregnant,

- b. have a positive urine pregnancy test result at Screening,
- c. intend to become pregnant during the study period,
- d. are breastfeeding.

Subjects who become pregnant during the study will not be discontinued;

- 2. Subjects currently participating in another investigational drug or device study.
- 3. History of clinically significant ocular co-morbidities that would affect surgical outcomes based on investigator expert medical opinion.
- 4. History of corneal refractive surgery.
- 5. Subjects who were targeted to monovision defined as ≥ 1.50 D of anisometropia.
- 6. Clinically significant PCO affecting vision.
- 7. History of Amblyopia or Monofixation syndrome with poor stereoscopic vision.

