10.2.3 Urine Pregnancy: Entry Criteria

Perform urine pregnancy test according to the manufacturer's procedure on female subjects of child-bearing potential.

10.2.4 Preoperative/Operative Chart Review Information: Entry Criteria and Effectiveness Assessment

From preoperative/operative chart review, collect and record the lens model implanted, the IOL power, biometry, keratometry, the predicted target residual refractive error for each eye, operating surgeon (first eye), 1st operative eye (OD/OS), date of surgery for second eye. Also collect the IOL calculation method used (e.g., Barrett) in each eye. If a separate Toric calculator was used in addition to the IOL power calculation, document the Toric calculator used in each eye.

Note: To qualify for study participation the subject must have the Clareon Vivity/Vivity Toric bilaterally or Clareon Monofocal/Toric bilaterally and an IOL spherical power must be within the 10.0 to 30.0 D range in both eyes and for both lens types. If a Toric lens was used, the cylinder power at the IOL plane must be in the range +1.50 to +3.75 Diopters in 0.75 D increments for each eye. A subject may have a Toric lens in one eye and a non-Toric in the fellow eye as long as the IOL type is matched (e.g., Clareon Vivity/Vivity Toric or Clareon Monofocal/Monofocal Toric).

Subjects who were targeted to monovision defined as ≥ 1.50 D of anisometropia do not qualify for the study and should be excluded.

Review for exclusion criteria.

If corneal topography and/or aberrometry are/is available in the chart, collect this information for each eye.

Refer to MOP for details.

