12.4 Effectiveness Analyses

12.4.1 Analysis of Primary Effectiveness Endpoints

The co-primary effectiveness objectives are:

- 1. To demonstrate that Clareon Vivity/Vivity Toric IOL is non-inferior to Clareon Monofocal/Clareon Toric IOL in mean binocular photopic best corrected distance visual acuity (BCDVA) at 3 to 6 months (90 to 180 days) postoperatively.
- To demonstrate that Clareon Vivity/Vivity Toric IOL is superior to Clareon Monofocal/Clareon Toric IOL in mean binocular photopic distance corrected intermediate visual acuity (DCIVA) (66 cm from spectacle plane) at 3 to 6 months (90 to 180 days) postoperatively.

The corresponding primary effectiveness endpoints are

- Binocular photopic BCDVA (logMAR) at 4 m.
- Binocular photopic DCIVA (logMAR) at 66 cm.

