12.4.2 Analysis of Secondary Effectiveness Endpoints

The secondary effectiveness objectives are:

- To demonstrate that Clareon Vivity/Vivity Toric IOL is superior to Clareon Monofocal/Clareon Toric IOL in mean binocular photopic distance corrected near visual acuity (DCNVA) (40 cm from spectacle plane) at 3 to 6 months (90 to 180 days) postoperatively.
- To demonstrate that Clareon Vivity/Vivity Toric IOL is superior to Clareon Monofocal/Clareon Toric IOL with respect to proportion of subjects who respond "Never" to Q1 of the IOLSAT questionnaire (Overall, in the past 7 days, how often did you need to wear eyeglasses to see?) at 3 to 6 months (90 to 180 days) postoperatively.

The corresponding secondary effectiveness endpoints are:

- Mean binocular photopic DCNVA (logMAR) at 40 cm.
- Proportion of subjects who respond "Never" to Q1 of the spectacle use questionnaire (IOLSAT)

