12.4.2.2 Analysis Methods

The FAS will be used for the primary statistical analyses for both endpoints.

Analysis of the first secondary endpoint (binocular DCNVA) will be based on a two sample ttest assuming equal variances with testing based on a one-sided lower tailed test conducted at the 0.05 significance level. A two sided 95% confidence interval for the difference in means (Clareon Vivity/Vivity Toric IOL minus Clareon/Clareon Toric IOL) will also be presented.

Analysis of the second secondary endpoint (Q1 for IOLSAT) will be based on a Chi-squared test of two proportions with testing based on a one-sided upper tailed test carried out at the 0.05 significant level. The proportion of subjects who respond "Never" to Q1 of the spectacle use questionnaire (IOLSAT) in each group will be presented.

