1.3 Randomization

This study is not randomized.

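### IOLSAT Q1 is the only one of the four tests not taken through distance correction, yet its visible superiority rule in this nonrandomised study makes no allowance for the recorded refractive target

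*SAP*

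**What the plan says.** Four hypotheses are tested. BCDVA is best corrected. The second endpoint is "distance corrected intermediate visual acuity (DCIVA) (66 cm from spectacle plane"), and DCNVA is likewise distance corrected (Protocol 12.4.1 and 12.4.2). The fourth is the proportion answering 'Never' to Q1: "Overall, in the past 7 days, how often did you need to wear eyeglasses to see"? Protocol 10.2.9 recommends completing this questionnaire before the manifest refraction.

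SAP 4.3.2.2 takes a two-sided 90% interval for the difference in proportions, which "will be calculated using the Miettinen-Nurminen method (1985), and Vivity IOL will be determined to be superior to Monofocal IOL" when the lower limit is above zero. Protocol 12.4.2.2 says the analysis "will be based on a Chi-squared test of two proportions", one-sided at 0.05. Neither names a covariate or stratum.

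SAP 1.3 states: "This study is not randomized". Protocol 10.2.4 collects "the predicted target residual refractive error for each eye" from the chart. The only visible entry limit on targeting is the exclusion of "Subjects who were targeted to monovision defined as ≥ 1.50 D of anisometropia" (Protocol 8.2). Protocol 12.3 plans by-group summaries of continuous baseline variables without naming the target, and the list in SAP 3 does not name it either.

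**The concern.** The chance of never needing glasses can depend on where the surgeon aimed the refraction as well as on the lens. The 1.50 D exclusion removes the largest planned offsets between eyes. Smaller offsets remain eligible, and so does a near-shift shared by both eyes. Lens and target were both chosen in practice before enrolment, so the mix of targets can differ between groups, and a crude difference would then carry that imbalance.

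The comparator was chosen "to support clinical benefit statements in which the performance of Clareon Vivity/Vivity Toric is compared to a monofocal IOL" (Protocol 7.4), and a Q1 superiority finding would naturally feed such a statement. An imbalance one way could produce superiority without a lens effect; the other way, it could hide a real one.

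**Working it through.** **Inputs from the documents.** 95 evaluable per arm; one-sided 5%; expected Q1 difference 0.14 with stated power above 96% (SAP 7). No 'Never' rate is given for either arm and nothing is said about the mix of targets, so every rate and share below is an assumption, shown over a range.

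**The plan's own figures.** BCDVA: (0.10 − 0.04)/(0.14 × √(2/95)) − 1.645 = 2.954 − 1.645 = 1.309, so power is 90.5%, matching the stated 90%. For Q1, power depends on the unstated comparator rate. I enumerated every pair of binomial counts and rejected when d/√[p̄(1−p̄)(2/n)·N/(N−1)] > 1.645, with n = 95, N = 190, d the observed difference and p̄ the pooled proportion. Power at +0.14 is:

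| Comparator rate | 3% | 5% | 10% | 20% | 50% |
|---|---|---|---|---|---|
| Power | 96.7% | 92.8% | 83.2% | 70.2% | 61.1% |

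It reaches 96% only at a comparator rate of about 3.4% or less or, by symmetry, about 82.6% or more. This says nothing about confounding, but it shows which rates fit the plan's figure.

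**No lens effect, shift in 'Never' caused by targeting (same enumeration).**

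| Comparator rate | 3% | 5% | 10% | 20% | 50% |
|---|---|---|---|---|---|
| No shift | 6.2% | 5.7% | 5.1% | 4.8% | 4.8% |
| 2 points | 19% | 15% | 11% | 9% | 8% |
| 4 points | 38% | 30% | 21% | 16% | 13% |

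Any 4-point bias gives these figures; they are not evidence about targeting itself.

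**How targeting could produce such a shift.** Assume 'Never' is 3% with a distance target and 30% with a near-shifted one, and that 40% of the Vivity group and 20% of the monofocal group are near-shifted.

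- Vivity: 0.6 × 0.03 + 0.4 × 0.30 = 13.8%.
- Monofocal: 0.8 × 0.03 + 0.2 × 0.30 = 8.4%.

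The rule then declares superiority 32% of the time with no lens effect, against about 5% if both shares are 20%.

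**The other direction.** With a true 14-point lens effect and a 4-point handicap, the expected difference is 10 points. Power falls from 97% to 86% at a 3% comparator rate, from 83% to 61% at 10% and from 70% to 48% at 20%.

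**Which adjustment works.** Assume one target value per subject, normal with SD 0.25 D and means of −0.4 D (Vivity) and −0.2 D (monofocal). Let the chance of 'Never' be 1% plus 20 points per dioptre of near shift, with no lens effect. Simulated false superiority:

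- crude: about 24%;
- two target classes, cut at −0.25, −0.50 or −0.75 D: about 9%, 11% and 18%;
- regression on lens group and continuous target, or three classes: 6% to 7%.

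Two classes leave much of the bias when the target is continuous.

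**Precision cost.** Adding a true 14-point lens effect to that model gives power of about 85% adjusted against 98% crude. The crude figure is inflated: average rates are about 23.1% and 5.6%, a difference of 17.5 points, of which 3.5 come from targeting.

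**The case against.** The strongest reply is that much of this may already be in hand. Protocol 12.3 plans by-group summaries of continuous baseline variables, and the predicted target is a continuous preoperative value, so a natural reading covers it. SAP 4.4 and 4.5 are not visible: the contents list runs from 4.3.2.2 on page 14 to 4.6 on page 20, with Table 4-1 on page 17. An adjusted analysis could sit there or in redacted text. Both points stand. They limit the claim to the visible rule and make the fix conditional.

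It can also be said that a target set after the lens is chosen is part of how that lens is used, so the crude contrast answers a legitimate as-used question. That stands too, and is why the crude rule should be kept. All four tests are unadjusted, but only Q1 leaves this recorded variable unneutralised.

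A reader might infer that Vivity eyes were aimed nearer and that Q1 is biased in their favour. No document shows any imbalance, its size or its direction.

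A reader might also infer that an adjusted interval excluding zero would credit the lens itself. It would not. With equal target shares and a 4-point imbalance from some other source, stratifying by target left false superiority at 37% against 38% crude (3% comparator rate). Subjects are also not masked, and Q1 is self-reported.

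**Conclusion.** The point holds as a minor improvement to the analysis of one endpoint. Q1 is the only tested endpoint not taken through distance correction, allocation is not random, the target is already collected, and the visible decision rule ignores it. The possible distortion is material on plausible assumptions (8% to 38% false superiority for a 2- to 4-point shift, against a nominal 5%). Its actual size and direction are unknown, since comparator rate, target mix and effect of target on 'Never' are all assumed.

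The documents do not support saying that the sponsor failed to plan any use of the target, or that the Q1 result will be wrong. Co-primary success (SAP 4) rests on BCDVA and DCIVA alone and is unaffected.

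**What to change.** Unless the text that is not visible already does this:

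1. In SAP 4.3.2.2, keep the crude Miettinen-Nurminen rule and prespecify beside it a target-adjusted difference in proportions with a 90% interval. Enter both eyes' recorded targets as continuous covariates, for example through a regression-standardised risk difference, rather than splitting them into two classes. Fix the model and variance method before unmasking and without reference to results by lens group, in keeping with Protocol 12. Include a fallback for sparse data: a 3% rate is about 3 of 95 subjects.
2. Name the predicted target, for each eye, among the by-group baseline summaries that Protocol 12.3 already plans.
3. Report Q1 superiority as a nonrandomised, as-used comparison. If the adjusted interval includes zero, say that targeting may explain the crude result. If it excludes zero, say only that the result is robust to recorded target.

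The cost is SAP wording, one extra output and one named baseline variable, with no new data. The adjusted interval loses precision when target and lens are associated, as in the 85% against 98% case above. It addresses imbalance in recorded target only.

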4.6 Handling of Missing Data

All key effectiveness endpoints are assessed at Visit 1 (90-180d post 2nd eye implant). The influence of missing data is expected to be minimal. Missing values for co-primary and secondary effectiveness endpoints by IOL group will be summarized. Missing values will not be imputed. [REDACTED]

4.7 Interim Analysis for Effectiveness

Not applicable.

5 SAFETY ANALYSIS STRATEGY

5.1 Safety Endpoints

The safety endpoints are:

- Adverse events
- Device deficiencies
- QUID subject survey

- Binocular and monocular (first eye implanted) mesopic contrast sensitivity test (with and without glare)
- IOP
- Slit lamp examination findings including:
 - IOL observations
 - Absolute IOL position change (tilt and decentration)
 - Subjective posterior capsular opacification (PCO)
 - Posterior capsulotomy rates
- Dilated fundus examination, including fundus visualization

5.2 Safety Hypotheses

There are no formal safety hypotheses in this study. The focus of the safety analysis will be a comprehensive descriptive assessment of safety endpoints listed in Section 5.1.

5.3 Statistical Methods for Safety Analyses

The focus of the safety analysis will be a comprehensive descriptive assessment of occurrence of adverse events and other safety parameters. Descriptive summaries (number and percentage) and listings will be presented. Individual subject listings will be provided for AEs that occur after signing informed consent. In addition to the specific requested variable/outcome of interest, all listings will include the following common variables (if appropriate): site, subject, age, sex, race, ethnicity, IOL group/model, visit, implant eye and eye.

5.3.1 Extent of Exposure

Retrospective exposure durations are collected at Visit 0 (screening visit) and will be summarized as a continuous measure (N, mean, median, standard deviation, minimum and maximum) by IOL group. Duration is defined as the day of Visit 1 minus the day of 2nd eye implant, plus 1.

5.3.2 Adverse Events

Adverse events are collected at both Visit 0 (screening visit) and Visit 1 (90-180d post 2nd eye implant).

Descriptive summaries (number and percentage) for all ocular adverse events will be presented by preferred term with a breakdown by IOL group, separately for first and second eyes. An eye with multiple ocular AEs of the same preferred term is only counted once toward the total of this preferred term.

The number and percentage of all adverse events will also be summarized with a breakdown by IOL group, separately for first and second implanted eyes.

Adverse events will be summarized in the following tables:

1. All Adverse Events (Serious and Non-Serious Combined)
 - a. Ocular
 - b. Nonocular
2. All Adverse Device Effects
 - a. Ocular
 - b. Nonocular
3. All Serious Adverse Events (including Serious Adverse Device Effects)
 - a. Ocular
 - b. Nonocular
4. Subject Listings
 - a. Non-Serious Ocular
 - b. Non-Serious Nonocular
 - c. Serious Ocular
 - d. Serious Nonocular

5.3.3 Device Deficiencies

Device deficiencies are collected at both Visit 0 (screening visit) and Visit 1 (90-180d post 2nd eye implant).

The number and percentage for each device deficiency category will be summarized with a breakdown by IOL group, separately for first and second implanted eyes. A listing of all device deficiencies, as recorded on the Device Deficiency Form, will also be provided.

5.3.4 QUVID Subject Survey

QUVID questionnaire will be conducted at Visit 1 (90-180d post 2nd eye implant).

Descriptive summaries (number and percentages) for the severe and most bothersome (separately) visual disturbances as presented by the subjects using the QUVID questionnaire

will be presented by IOL group. These rates will be accompanied by two-sided exact 95% confidence intervals.

Descriptive summaries (number and percentage) for each category of responses to each question on the QUID questionnaire will be presented by IOL group.

